Appendix H Procedures at CRS for Part A

Visit	01 ¹	02 ²	03	04	05	06	07	08	Post
Day		D1	D4	D7	D29	D57	D113	D169	
Week		W0	W0	W0	W4	W8	W16	W24	
Procedure	Scr	Inf							
Study procedures									
Signed screening consent (if used)	Х								—
Assessment of Understanding (AoU)	Х								
Signed protocol consent	Х								—
Medical history	Х								
Complete physical exam	Х							Х	
Confirm eligibility, obtain demographics	Х								
Infusion		Х							
Solicited AE assessment ³	_	X ³	X ³	X ³	—	—	—		—
Abbreviated physical exam	_	Х	Х	Х	Х	Х	Х		
Risk-reduction counseling ⁴	Х	Х		—	Х	Х	Х	Х	
Contraception status assessment ⁵	Х	Х			Х	Х	Х	Х	
Social impact assessment	_	Х			Х	Х	Х	Х	—
Behavioral assessment questionnaire ⁶	Х							Х	
Social impact assessment questionnaire						Х		Х	
Acceptability questionnaire	_	Х							
Outside testing and belief questionnaire								Х	
Concomitant medications	Х	Х	Х	Х	Х	Х	Х	Х	
Intercurrent illness/unsolicited AE assessment		Х	Х	Х	Х	Х	Х	Х	_
HIV assessment ⁷	Х						Х	Х	
Confirm HIV test results provided to participant		Х						Х	Х
Specimen collection ⁸	Х	Х	Х	Х	Х	Х	X	Х	

HVTN 143/HPTN 109 Version 1.0 / June 07, 2023

Footnotes for Appendix H:

¹ Screening may occur over the course of several contacts/visits, up to and including day 1 prior to study-product administration.

- ² Specimens collected at day 1 may be obtained within the 14 days prior to study-product administration, except for a pregnancy test, which must be performed on urine or blood specimens within 48 hours prior to study-product administration.
- ³ Solicited adverse event (AE) assessments are performed daily for at least 3 full days following study-product administration. Clinical research site (CRS) staff will review and reconcile the diary with the participant and then report solicited AEs. Participant diary reconciliation may happen as the data is available (see the HVTN 143/HPTN 109 study-specific procedures [SSP]).

⁴ Includes transmission risk-reduction counseling for participants living with HIV.

⁵ Contraception status assessment is required only for participants who are of pregnancy potential.

⁶ Not applicable to participants living with HIV.

⁷ Includes pretest counseling and HIV testing. A subsequent follow-up contact is conducted to provide post-test counseling and to report results to participant. Not applicable for participants diagnosed with HIV.

⁸ For specimen collection requirements, see Appendix F.

Appendix I Procedures at CRS for Part B

Visit	01 ¹	02 ²	03	04	05	06	07	08	09	10	11	12	Post
Day		D1	D4	D7	D29	D57	D113	D169	D173	D225	D304	D365	
Week		W0	W0	W0	W4	W8	W16	W24	W24	W32	W40	W48	
Procedure	Scr	Inf 1						Inf 2	Phone contact				
Study procedures													
Signed screening consent (if used)	Х	—	—							_			
Assessment of Understanding (AoU)	Х		_		_								_
Signed protocol consent	Х		_		_								_
Medical history	Х		_		_								
Complete physical exam	Х	_				_						Х	
Confirm eligibility, obtain demographics, randomize	Х	_			_	_				_		_	_
Infusion		Х	_					Х		—	—	—	
Solicited AE assessment ³		X ³	X ³	X ³				X ³	X ³				
Abbreviated physical exam		Х	Х	Х	Х	Х	Х	Х		Х	Х	—	—
Risk-reduction counseling ⁴	Х	Х	—	—	Х	Х	Х	Х		Х	Х	Х	—
Contraception status assessment ⁵	Х	Х	—	—	Х	Х	Х	Х		Х	Х	Х	—
Social impact assessment		Х	—	—	Х	Х	Х	Х		Х	Х	Х	—
Behavioral assessment questionnaire ⁶	Х		—							_		Х	—
Social impact assessment questionnaire			—			Х				_		Х	—
Acceptability questionnaire		Х	—		—			Х		_			—
Outside testing and belief questionnaire			_		_							Х	
Concomitant medications	Х	Х	Х	Х	Х	Х	Х	Х		Х	Х	Х	—
Intercurrent illness/unsolicited AE assessment		Х	Х	Х	Х	Х	Х	Х		Х	X	Х	
HIV assessment ⁷	Х						Х			Х		X	
Confirm HIV test results provided to participant		Х										X	Х
Specimen collection ⁸	Х	Х	Х	Х	Х	Х	Х	Х		Х	Х	Х	
Footnotes for Appendix I:

¹ Screening may occur over the course of several contacts/visits, up to and including day 1 prior to study-product administration.

- ² Specimens collected at day 1 may be obtained within the 14 days prior to study-product administration, except for a pregnancy test, which must be performed on urine or blood specimens within 48 hours prior to study-product administration.
- ³ Solicited adverse event (AE) assessments are performed daily for at least 3 full days following study-product administration. CRS staff will review and reconcile the diary with the participant and then report solicited AEs. Participant diary reconciliation may happen as the data is available (see the HVTN 143/HPTN 109 study-specific procedures [SSP]). For Part B participants' second infusion solicited AE data collection: remote documentation of the participant diary may occur after the solicited AE assessment period and the next clinic visit (visit 9) (see the HVTN 143/HPTN 109 SSP).
- ⁴ Includes transmission risk-reduction counseling for participants living with HIV.
- ⁵ Contraception status assessment is required only for participants who are of pregnancy potential.
- ⁶ Not applicable to participants living with HIV.
- ⁷ Includes pretest counseling and HIV testing. A subsequent follow-up contact is conducted to provide post-test counseling and to report results to participant. Not applicable for participants diagnosed with HIV.
- ⁸ For specimen collection requirements, see Appendix G.

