9.3 Enrollment and study-product administration visits

Once a volunteer has consented to trial participation and is found to meet all eligibility criteria (see Sections 7.1 and 7.2), the CRS requests the randomization assignment via a Web-based randomization system. Enrollment is simultaneous with first study-product administration. In general, the time interval between randomization and enrollment should not exceed 4 working days. However, circumstances may require a participant's enrollment visit to be changed. This may exceed the 4-day randomization time limit with approval from the clinical trial manager/clinical research manager.

At all study-product administration visits, the following procedures are performed before study-product administration:

- Abbreviated physical examination, including weight, vital signs, and a symptom-directed evaluation by history and/or appropriate physical exam based on participant self-reported symptoms or complaints;
- Assessment of baseline solicited AEs;
- Assessment of concomitant medications (as described in Section 9.2);
- Assessment of any new or unresolved unsolicited AEs/intercurrent illnesses; and
- Clinical laboratory tests including:
 - CBC with differential;
 - Chemistry panel (ALT, aspartate aminotransferase [AST], alkaline phosphatase [Alk Phos], and creatinine); and
 - Urine or serum pregnancy test (for participants who are of pregnancy potential). Persons who are NOT of pregnancy potential due to having undergone hysterectomy or bilateral oophorectomy (verified by medical records), are not required to undergo pregnancy testing. For pregnant participants, see Section 9.11.

Following completion of all procedures in the preceding list, and if available results indicate that study-product administration may proceed, study product is administered (see Sections 8.3 and 8.4).

Administration of all infusions during a study-product administration visit must be accomplished within 1 calendar day.

Immediately following study-product administration, the participant remains in the clinic for observation for about 1 hour. See the HVTN 143/HPTN 109 SSP for details regarding study-product administration visit procedures. Before leaving the clinic, the participant is given the Participant Diary and is instructed on how to complete it. The CRS will make arrangements to be in contact with the participant as described in Section 9.8.

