The following procedures will be performed at **all study-product administration visits**. These procedures may be performed **prior to or following study-product administration**:

- Risk-reduction counseling (as described in Section 9.5);
- For participants of pregnancy potential, contraception status assessment (as described in Sections 9.2 and 9.6). For persons who are confirmed pregnant, contraception status assessment is not required; and
- Assessment of new or unresolved social impacts (CRS staff will ask participant about the status of any unresolved social impacts and if they have experienced any new social impacts as a result of the trial participation).

The following procedures will be performed at all infusion visits following studyproduct administration:

- Acceptability questionnaire (see Appendix H and Appendix I); and
- Drug concentrations/detection collection (see Appendix F and Appendix G).

Additional procedures will be performed at scheduled visits as specified in Appendix H and Appendix I:

- HIV assessment, including pretest counseling and HIV testing. A subsequent follow-up contact is conducted to provide post-test counseling and to report results to participant;
- Confirm that participants received HIV test results from previous visit. If not, provide test results and post-test counseling as appropriate; and
- Specimen collection (should be completed per Appendix F and Appendix G).

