9.4 Follow-up visits

The following procedures are performed at **scheduled follow-up visits**, as specified in Appendix H and Appendix I:

- Risk-reduction counseling (as described in Section 9.5);
- For participants of pregnancy potential, contraception status assessment (as described in Sections 9.2 and 9.6). In persons who are confirmed pregnant, contraception status assessment is not required;
- Assessment of new or unresolved social impacts (CRS staff will ask participant about the status of any unresolved social impacts and if they have experienced any new social impacts as a result of the trial participation);
- Assessment of new or continuing concomitant medications (as described in Section 9.2);
- Assessment of new or unresolved AEs/intercurrent illnesses;
- Administration of the social impact assessment questionnaire (types of impacts assessed involve personal relationships, health insurance, life insurance, educational or employment opportunities, housing, immigration, or travel);
- Administration of a questionnaire that asks the participant about any HIV testing they may have received outside of the study;
- HIV assessment, including pretest counseling and HIV testing. A subsequent follow-up contact is conducted to provide post-test counseling and to report results to participant;

- Confirm that participants received HIV test results from previous visit. If not, provide test results and post-test counseling as appropriate;
- Abbreviated physical examination, including weight, vital signs, and a symptom-directed evaluation by history and/or appropriate physical exam based on participant self-reported symptoms or complaints;
- Complete physical examination, including weight and vital signs, and clinical assessments of head, ears, eyes, nose, and throat; neck; lymph nodes; heart; chest; abdomen; extremities; neurological function; and skin;
- Specimen collection (should be completed per Appendix F and Appendix G); and
- Clinical laboratory tests including:
 - CBC with differential;
 - Chemistry panel (ALT, AST, Alk Phos, and creatinine);
 - Urine dipstick (urinalysis if appropriate; see Section 9.7); and

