Appendix K Visit windows

Visit number	Visit type	Lower allowable window	Lower target day	Target day	Upper target day	Upper allowable window
1	Screening	-56	-		-	-
2	Enrollment ¹ Infusion	-	-	1	-	-
3	3 days post infusion	-1	-	4	-	+1
4	6 days post infusion	-1	-	7	-	+2
5	4 weeks post infusion	-7	-3	29	+3	+7
6	8 weeks post infusion	-7	-3	57	+3	+7
7	16 weeks post infusion	-7	-3	113	+3	+7
8	24 weeks post infusion	-7	-3	169	+3	+7

Part A

Part B

Visit number	Visit type	Lower allowable window	Lower target day	Target day	Upper target day	Upper allowable window
1	Screening	-56	-		-	-
2	Enrollment Infusion #1	-	-	1	-	-
3	3 days post infusion #1	-1	-	4	-	+1
4	6 days post infusion #1	-1	-	7	-	+2
5	4 weeks post infusion #1	-7	-3	29	+3	+7
6	8 weeks post infusion #1	-7	-3	57	+3	+7
7	16 weeks post infusion #1	-7	-3	113	+3	+7
8	Infusion #2	-14	-7	169	+7	+14
9	4 days post infusion #2	-	-	173	+7	-
10	32 weeks post infusion #2	-7	-3	225	+3	+7
11	40 weeks post infusion #2	-7	-3	304	+3	+7
12	48 weeks post infusion #2	-7	-3	365	+3	+7

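### Part B's procedure table omits, at D169 and D304, the check that participants received their D113 and D225 HIV results

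*Protocol*

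**What the plan says.** Two places in the protocol text describe the step. Section 9.4 on follow-up visits has "Confirm that participants received HIV test results from previous visit", and Section 9.3 on infusion visits uses the same words. Both add what staff must do when the check fails: "If not, provide test results and post-test counseling as appropriate". Neither section names visits. Section 9.3 hands the timing over: "Additional procedures will be performed at scheduled visits as specified in Appendix H and Appendix I". Section 9.4 likewise points to those appendices.

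In Appendix I (Part B) the row "HIV assessment" is ticked at screening, D113, D225 and D365. The row "Confirm HIV test results provided to participant" is ticked at D1, D365 and Post, and nowhere else.

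Footnote 7 of Appendix I sets the first route for returning every result: "A subsequent follow-up contact is conducted to provide post-test counseling and to report results to participant".

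**The concern.** The confirmation row is the protocol's own backstop. If the contact in footnote 7 did not happen, the row obliges staff to give the result and the counseling at the visit itself. To do that job it has to sit at the visit after each test. In Part B it sits there for the screening test (checked at D1) and for the D365 test (checked at Post), but not for the two tests in between.

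At stake is later disclosure, counseling and referral for a participant whose results contact failed. Section 9.6 has staff advise participants to test for HIV only through the site while on study, so for those who comply the trial is their only source of results.

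The point does not extend to dosing. The row is about the participant receiving the result, not about the site reviewing it. Section 9.3 allows infusion only "if available results indicate that study-product administration may proceed", and Sections 7.3.3 and 9.13 stop product once HIV acquisition is known.

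**Working it through.** **Inputs.** Test and confirmation visits come from Appendix I. The HIV-test visits agree with Appendix G, which draws a 10 mL HIV diagnostics tube at D113, D225 and D365. Windows come from Appendix K: D113 ±7, D169 ±14, D225 ±7, D304 ±7 and D365 ±7 days. D173 is a phone contact and is not counted as a clinic visit.

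**Step 1: match each test to the next clinic visit and to the next tick.**

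| HIV test | Next clinic visit | Next confirmation tick |
|---|---|---|
| Screening | D1 | D1 |
| D113 | D169 | D365 |
| D225 | D304 | D365 |
| D365 | Post | Post |

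The first and last rows line up. The two middle rows do not.

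**Step 2: try the readings of the previous-visit wording.**

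- Immediately preceding visit: D113 and D225 are both missed, and the D365 tick looks back to D304, where no HIV test is done. Two of the three on-study tests lack the step.
- Previous HIV-test visit: D365 covers D225, but D113 is still missed. One of three lacks the step.
- All results to date: D365 covers both, so none is left out, but this drops the previous-visit wording. Step 3 shows the wait that follows.

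**Step 3: wait to the next scheduled check if the results contact failed, by printed target days.** The range adds the two visits' windows.

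- D113 to D365: 365 − 113 = 252 days; 252 ± (7 + 7) gives 238 to 266.
- D113 to D169: 169 − 113 = 56 days; 56 ± (7 + 14) gives 35 to 77.
- D225 to D365: 365 − 225 = 140 days; 140 ± (7 + 7) gives 126 to 154.
- D225 to D304: 304 − 225 = 79 days; 79 ± (7 + 7) gives 65 to 93.

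Added wait: 252 − 56 = 196 days for D113, and 140 − 79 = 61 days for D225.

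**Step 4: repeat on the week labels.** The printed D304 and D365 do not fit their W40 and W48 labels; Appendix K, for example, prints target day 365 against "48 weeks post infusion #2". The other late visits follow day = 7 × week + 1 (W16 = 113, W24 = 169, W32 = 225). On that scale W40 = 281 and W48 = 337.

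- D113 to W48: 337 − 113 = 224 days (210 to 238), against 56.
- D225 to W48: 337 − 225 = 112 days (98 to 126), against 281 − 225 = 56 (42 to 70).

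Added wait: 224 − 56 = 168 days for D113, and 112 − 56 = 56 days for D225.

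**Step 5: participants on this schedule.** Groups 4 to 7 have 8 each and Group 8 has 30: 4 × 8 + 30 = 62.

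**The case against.** The best defence is that the text fixes no visits. Sections 9.3 and 9.4 leave timing to the appendices, and the Appendix I row label does not mention a previous visit. Ticks at entry, final visit and Post could be a deliberate entry-and-exit check, and Appendix H has the same three ticks for Part A. This places the fault in Appendix I but does not remove it. A schedule that first looks at the D113 result at the final visit does not carry out a step defined by the previous visit. Part A settles nothing either way: Appendix H ticks an HIV assessment at D113, but the Appendix F 56-day blood total there (95 mL = 52.5 + 42.5) appears to leave no room for an HIV tube.

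The second defence is that results reach participants by other routes. Footnote 7 requires a contact after every test. Section 9.5 has anyone found to have HIV referred for care. Risk-reduction counseling is scheduled at D169, D225 and D304, and D225 brings a new HIV assessment at which an undelivered D113 result might well surface. All of this stands, and it is why the waits above are upper-end figures for a failed contact. None of these routes obliges staff to ask whether the earlier result was received, which is the purpose of the confirmation row.

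Third, the study-specific procedures may add a check at D169. They are not available here, and Section 9.3 names the appendices as the schedule for this step.

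**Conclusion.** The point holds as an internal inconsistency and is minor. Appendix I leaves out the confirmation step at D169 and D304, where the wording of Sections 9.3 and 9.4 would put it. One or two of the three on-study HIV tests per Part B participant lack the step on either reading that keeps the previous-visit wording. If D365 is instead taken as a catch-all, no test is left out, but the check comes late.

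For a participant whose results contact failed, the added wait to the next scheduled check is 168 to 196 days for the D113 result and 56 to 61 days for the D225 result. The spread reflects whether the week labels or the printed days are right. These figures assume that the result does not surface at an intervening visit. The failure rate is not stated, and in a population selected for low likelihood of HIV acquisition few people should be affected. No statistical quantity in the trial is touched.

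**What to change.** Issue a clarification memo to Appendix I that ticks the confirmation row at visit 8 (D169, among the checks before infusion #2) and at visit 11 (D304). Keep the Post tick for the D365 test. Keep the D365 tick only as a catch-up for any earlier result still unconfirmed.

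Each interim test would then be followed by a check at the next in-person visit. The cost is two ticks at visits that already take place: no extra blood, visit or staff.

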Appendix J South African Guidelines for determining low likelihood of acquiring HIV

The following are intended as guidelines for the investigator to help identify potential trial participants with allow likelihood of acquiring HIV. These guidelines are based on behaviors within the last 12 months prior to enrollment; however, it may be appropriate to consider a volunteer's behavior over a longer period of time to effectively assess the volunteer's likelihood of acquiring HIV. Some volunteers may not be appropriate for enrollment even if they meet these guidelines. These guidelines should be supplemented and interpreted with local epidemiological information about HIV prevalence in your area and community networks. The investigator may review with the site Principal Investigator (PI) and/or the Protocol Safety Review Team (PSRT) a volunteer's likelihood of acquiring HIV.

Consider whether a volunteer would be appropriate for inclusion if, in the 12 months prior to enrollment, the person:

- Abstained from penile-vaginal and penile-anal intercourse, OR
- Was in a mutually monogamous relationship with a partner known to be living without HIV status, OR
- Had 1 partner known or believed to be living without HIV, with whom they regularly used condoms for penile-vaginal or penile-anal intercourse.

Exclude a volunteer if:

Within the 12 months prior to enrollment, a history of newly acquired syphilis; gonorrhea; chlamydia; trichomoniasis; active herpes simplex virus type 2 (HSV) lesions; chancroid; genital warts of the labia minora, vagina, or cervix; or any other symptomatic genital warts.

Appendix K Visit windows

Visit number	Visit type	Lower allowable window	Lower target day	Target day	Upper target day	Upper allowable window
1	Screening	-56	-		-	-
2	Enrollment ¹ Infusion	-	-	1	-	-
3	3 days post infusion	-1	-	4	-	+1
4	6 days post infusion	-1	-	7	-	+2
5	4 weeks post infusion	-7	-3	29	+3	+7
6	8 weeks post infusion	-7	-3	57	+3	+7
7	16 weeks post infusion	-7	-3	113	+3	+7
8	24 weeks post infusion	-7	-3	169	+3	+7

Part A

Part B

Visit number	Visit type	Lower allowable window	Lower target day	Target day	Upper target day	Upper allowable window
1	Screening	-56	-		-	-
2	Enrollment Infusion #1	-	-	1	-	-
3	3 days post infusion #1	-1	-	4	-	+1
4	6 days post infusion #1	-1	-	7	-	+2
5	4 weeks post infusion #1	-7	-3	29	+3	+7
6	8 weeks post infusion #1	-7	-3	57	+3	+7
7	16 weeks post infusion #1	-7	-3	113	+3	+7
8	Infusion #2	-14	-7	169	+7	+14
9	4 days post infusion #2	-	-	173	+7	-
10	32 weeks post infusion #2	-7	-3	225	+3	+7
11	40 weeks post infusion #2	-7	-3	304	+3	+7
12	48 weeks post infusion #2	-7	-3	365	+3	+7

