participants will receive 2 doses 6 months apart of VRC01.23LS + PGT121.414.LS + PGDM1400LS administered in combination with weight-based dosing as follows: 5 + 5 + 5 mg/kg IV, 20 + 5 + 5 mg/kg IV, 20 + 20 + 20 mg/kg IV, 40 + 5 + 5 mg/kg IV, and 40 + 40 + 40 mg/kg IV (Groups 4-8). Participants will be followed for 6 months in Part A and 12 months in Part B.

Figure 4-2 Breadth and potency curves for PGT121, PGDM1400, VRC01, VRC01.23LS, and 2 triple combinations (PGT121 + PGDM1400 + VRC01 and PGT121 + PGDM1400 + VRC01.23LS) to a panel of 108 viruses (61 from Clade B and 47 from Clade C) from the placebo arm in the AMP trials.

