6.4.4.1 Primary analyses of mAb concentrations

The primary analysis of serum concentration and PK of VRC01.23LS, PGDM1400LS, and PGT121.414.LS (primary objective 2) will be restricted to participants who received all scheduled administrations PP. Serum concentrations that fail the quality control of the assay, are from specimens collected outside of the visit window, or are from participants with HIV postacquisition may be excluded. The primary analysis of serum concentration will be descriptive and performed separately for each mAb. As an exploratory analysis, we will consider a pooled analysis across different dosing arms and investigate if the PK is modified by the dose. We will also compare the PK of VRC01.23LS administered alone with that of VRC01.23LS administered in combination with PGDM1400LS, and PGT121.414.LS.

A noncompartmental PK analysis will be performed on the concentration data. PK parameters may include, but are not limited to: AUC, Cmax, time to Cmax (Tmax), CL, Vd, terminal elimination rate constant (λz), and the terminal t1/2. Data will be summarized by each dose group and overall for CL, Vd, and t1/2. The potential for nonlinear PK will be determined by comparing the dose-adjusted ratios for Cmax and AUC within dosing groups. Graphical displays of the data (eg, boxplots, scatterplots, histograms, spaghetti plots) will be generated to visually explore distributional properties of the data. These summary statistics and graphical displays may be produced for each treatment arm and each timepoint separately. These summary statistics and PK parameters including half-life, will be compared to the published results of VRC01, VRC01LS, and VRC07-523LS.

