Appendix G Laboratory procedures for Part B

				11:- 4	4		-			-	7 -	0	•	40	44	40
				Visit	1 Screening	2	3	4	5	6		8	9	10	11	12
				Day:	visit ³	D1	D4	D7	D29	D57	D113	D169	D173 ¹⁶	D225	D304	D365
				Week:		W0			W4	W8	W16	W24		W32	W40	W48
						Study Product Administration #1					000000000000000000000000000000000000000	Study Product Administration #2				
				Tube size		VRC01.23LS +						VRC01.23LS +	1			
		Assay	Tube	(vol.		PGT121.414.LS +						PGT121.414.LS +				
Procedure	Ship to ¹	location ²	Type⁴	capacity)4		PGDM1400LS						PGDM1400LS				
BLOOD COLLECTION																-
Screening/Diagnostic																
Screening HIV test	Local lab	Local lab	EDTA	5mL	5	_	—	—	—	—	—	_	I —	_	—	_
HBsAg/anti-HCV	Local lab	Local lab	SST	5mL	5		—	—	—	—	—		—	—	—	—
Syphilis ⁹	Local lab	Local lab	SST	5mL	5	—	_	—	_	—	—	_	_		_	
HIV diagnostics ⁷	HSML-NICD	HSML-NICD	EDTA	10mL	—	—	-	—	—	—	10	_		10	—	10
Safety labs ¹⁰																
CBC/ Differential	Local lab	Local lab	EDTA	5mL	5	5	—	—	—	5	—	5	I —	5	_	5
Chemistry Panel ⁵	Local lab	Local lab	SST	5mL	5	5	-	—	—	5	—	5	—	5	—	5
Drug concentrations/detection							.,		,							
VRC01.23LS, PGT121.414.LS and PGDM1400LS concentration	CSR	HVTN Labs	SST	8.5mL	_	у	У	у	У	у	у	у	_	у	у	у
1 hour Post Study Product Administration VRC01.23LS, PGT121.414.LS and PGDM1400LS concentration ¹⁴	CSR	HVTN Labs	SST	8.5mL	_	8.5	_		_		_	8.5	_	_	_	
Humoral assays																
HIV-1 neutralizing Ab	CSR	HVTN Labs	SST	8.5mL	_	у	у	у	у	у	у	у	—	у	у	у
Non-neutralizing antiviral assays ¹⁷	CSR	HVTN Labs	SST	8.5mL	_	у	у	у	у	у	у	У	—	у	у	у
Anti-Drug Antibody (ADA)																
ADA detection assays (screening, confirmatory, titration)	CSR	HVTN Labs	SST	8.5mL	_	У	_	—	-		у		_	_	у	у
ADA functional assay	CSR	HVTN Labs	SST	8.5mL	_	y					y	—	—		y	y
Ab Reaction ¹¹							*******	£			×	5				h
Tryptase / C3 and C4 Complement / Cytokines	CSR	ARUP	SST	8.5mL	_					S	See foo	tnote 12				
ADA detection assays (screening, confirmatory, titration)	CSR	HVTN Labs	SST	8.5mL	_	See footnote y	_		—	_	—	See footnote y	_	_	_	—
ADA functional assay	CSR	HVTN Labs	SST	8.5mL	—	See footnote y	—	—	—	—	—	See footnote y	—	—	—	—
STORAGE	****															
Serum	CSR	_	SST	8.5mL		68.0	42.5	42.5	42.5	42.5	42.5	42.5		42.5	42.5	42.5
Visit total					25	86.5	42.5	42.5	42.5	52.5	53	61.0	0	62.5	42.5	62.5
56-Day total ¹³					25	112	154	197	239	292	53	114	61	124	105	168
																ļ
Urine dipstick ⁸	Local lab	Local lab			Х					Х	 	_				X

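### Part B visits 10 to 12 carry target days, week headings and post-infusion labels that disagree, and visits 9 to 12 have no stated anchor to infusion #2

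*Protocol*

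**What the plan says.** **Appendix K, Part B.** Infusion #2 (visit 8) has target day 169 and an allowable window of ±14 days. Visit 9, "4 days post infusion #2", has target day 173; its only stated limit is +7, in the upper target column. Visits 10, 11 and 12 are labelled "32 weeks post infusion #2", "40 weeks post infusion #2" and "48 weeks post infusion #2". Their target days are 225, 304 and 365, each with an allowable window of ±7 days.

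**Appendices G and I.** Both give the same days for visits 10 to 12 ("D225 D304 D365" in Appendix G) under the headings W32, W40 and W48. Appendix G, footnote 16, makes visit 9 a phone contact without specimens.

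**Section 4.1.1.** "Participants will be followed for 6 months in Part A and 12 months in Part B".

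**Sections 6.4 and 6.4.4.1.** The primary analyses of concentration and antiviral activity are per-protocol, and that population is defined with reference to the expected visit window. Section 6.4.4.1 adds that concentrations that "are from specimens collected outside of the visit window" may be excluded.

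**The concern.** The post-infusion label, the week heading and the target day should describe the same moment. At visits 11 and 12 all three differ. At visit 10 the day and the week agree, and only the post-infusion label conflicts.

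These visits matter because, after the 1-hour draw on the day of infusion #2, they supply every repeat-dose sample for concentration and neutralization (primary objectives 2 and 3). If a site schedules from a conflicting heading or label, the sample falls outside a ±7-day window and its concentration may be excluded from the primary analysis. If an analyst takes elapsed time from the label, the time since dosing is wrong. A drawn sample cannot be re-timed.

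A second question is what the days are counted from. Infusion #2 may move by two weeks either way, but the visits after it are listed as study days with no rule for moving them.

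**Working it through.** **Inputs.** Target days, labels and windows are from Appendix K, Part B, and week headings from Appendices G and I. The 70-day half-life is the one assumed in Section 4.2.2 for PGDM1400LS and PGT121.414.LS; for VRC01.23LS that section relies on 71 ± 18 days.

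**1. The rule for earlier visits.** Day = 7 × week + 1 gives W4 = 29, W8 = 57, W16 = 113 (Appendix K: "16 weeks post infusion #1", day 113) and W24 = 169. All match. The visit 9 label also works when counted from infusion #2: 169 + 4 = 173.

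**2. Visits 10 to 12 on each reading.** Study week: 7 × week + 1. Post-infusion label: 169 + 7 × weeks.

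| Visit | Listed day | Day from week heading | Gap | Day from post-infusion label | Gap |
|---|---|---|---|---|---|
| 10 | 225 | 7×32+1 = 225 | 0 | 169+224 = 393 | 168 |
| 11 | 304 | 7×40+1 = 281 | 23 | 169+280 = 449 | 145 |
| 12 | 365 | 7×48+1 = 337 | 28 | 169+336 = 505 | 140 |

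Every gap except visit 10 against its week heading exceeds 7 days.

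**3. What the listed days are.** From infusion #2: (225−169)/7 = 8.0, (304−169)/7 = 19.3 and (365−169)/7 = 28.0 weeks. From enrollment: (225−1)/7 = 32.0, (304−1)/7 = 43.3 and (365−1)/7 = 52.0 weeks.

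**4. Against stated follow-up.** 365/30.44 = 12.0 months, which fits. 505/30.44 = 16.6 months, which does not.

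**5. Anchor.** Infusion #2 is in window on days 169 − 14 = 155 to 169 + 14 = 183. Visit 9, read as a fixed study day, ends at 173 + 7 = 180. An infusion on days 181 to 183 would be in window yet later than its own follow-up contact. Visit 10 at day 225 falls 225 − 183 = 42 to 225 − 155 = 70 days after dosing.

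With a 70-day half-life, the second dose's contribution varies by 2^(28/70) = 1.32-fold over that range. Half-lives of 53 and 89 days (71 ± 18) give 2^(28/53) = 1.44 and 2^(28/89) = 1.24. The residue of the first dose is fixed at day 225 and dilutes this. For equal doses and simple exponential decline, that residue is 2^(−224/70) = 0.109 of the initial level. The total then varies by (2^(−42/70) + 0.109)/(2^(−70/70) + 0.109) = 0.769/0.609 = 1.26-fold.

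**The case against.** The strongest reply is that the scheduling target is clear. All three appendices list days 225, 304 and 365, the Appendix K windows belong to the target-day column, and day 365 fits the stated 12 months. On this view the post-infusion wording is a slip for weeks since enrollment, and no site would hold visit 12 at day 505. Much of this stands: the 140- to 168-day figures are gaps between a label and a target day, not expected sampling errors. It does not remove the 23- and 28-day conflicts at visits 11 and 12, because those arise when weeks are counted from enrollment.

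The exclusion in Section 6.4.4.1 is permissive. Sections 6.4 and 6.4.5.2 already provide for actual collection and dosing times in secondary and PK/PD analyses. How the primary analysis handles time may be in the SAP, and handling of out-of-window visits is referred to the study-specific procedures; neither is at hand. The anchor point is therefore an unstated rule, and the fold ranges assume that visits are not moved with the infusion.

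Two stronger readings are tempting:

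- **The blood totals show that day 281 was meant.** Appendix G's 56-day total of 105 mL at D304 is 62.5 + 42.5, so it counts D225, 79 days earlier. But the 168 mL at D365 is 62.5 + 42.5 + 62.5 = 167.5, which also counts D225, 140 days before D365 and 112 before day 337. The D113 entry (53) omits a visit exactly 56 days earlier, while the D169 entry (114) includes one. The row fits no single clock. The largest listed total, 292 mL, is well under the 500 mL limit.
- **A planned comparison with 16 and 24 weeks after infusion 1 is biased.** The protocol specifies no such comparison. Primary concentration analysis is descriptive, by group and timepoint.

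**Conclusion.** The schedule is wrong as written and needs reconciling.

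- The post-infusion labels at visits 10 to 12 miss the listed target days by 168, 145 and 140 days.
- The week headings agree at visit 10 but miss by 23 and 28 days at visits 11 and 12, beyond the ±7-day windows.
- No anchor is stated for visits 9 to 12. If they are fixed study days, visit 9 can precede an in-window infusion, and time from dosing to visit 10 ranges over 28 days. That is 1.32-fold in the second dose's contribution at the assumed 70-day half-life, or about 1.26-fold in the total under simple exponential decline with equal doses.

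The calendar results use only the protocol's own days and the rule that its earlier visits follow. The loss is conditional: it arises only where someone works from a conflicting label or heading, or where visits are not re-timed to the infusion. The documents do not show that samples will be lost, and they do not settle which schedule was intended.

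**What to change.** Reconcile Appendices G, I and K so that each of visits 9 to 12 has one target day, one matching week label and one stated anchor, either enrollment or the actual date of infusion #2. Recompute the windows and the 56-day blood totals to match. The protocol team must decide which schedule is meant.

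State also that post-infusion-2 concentrations and neutralization are summarized by actual days since infusion #2 in the primary analysis, as the secondary analyses already allow; if the SAP says so, a cross-reference is enough.

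The cost is a clarification memo or letter of amendment, best issued before Part B opens. Reconciling the text requires no extra visits or samples.
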